11.6.1.2 SECONDARY AND EXPLORATORY EFFICACY OUTCOMES

Other efficacy outcomes include: time to undetectable minimal residual disease, overall response rate (ORR), complete response (CR) rate, progression free survival (PFS), time to second objective disease progression (PFS-2), [REDACTED], duration of peripheral blood U-MRD response, and treatment free survival (TFS).

11.6.1.2.1 TIME TO UNDETECTABLE MINIMAL RESIDUAL DISEASE

Time to undetectable minimal residual disease is defined as the interval from enrollment to the first assessment of U-MRD. It will be estimated by the Kaplan Meier method. For subjects who do not achieve U-MRD, it will be censored at the last MRD assessment.

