Following screening, qualified subjects will add ublituximab and umbralisib to their existing ibrutinib, acalabrutinib or venetoclax treatment. Any therapy previously given concurrently with ibrutinib, acalabrutinib or venetoclax, including anti-CD20 therapy, must have been discontinued 21 days prior to Day 1 of Cycle 1 (See Exclusion Criterion #1). Determination of enrollment in Cohort A versus Cohort B or Cohort C will depend on which agent the subject was receiving prior to screening (ibrutinib, acalabrutinib or venetoclax).

Three cohorts will be studied:

- **Cohort A:** ublituximab and umbralisib with ibrutinib
- **Cohort B:** ublituximab and umbralisib with venetoclax
- **Cohort C:** ublituximab and umbralisib with acalabrutinib

Up to approximately 28 subjects may be enrolled into each cohort.

Study Duration

MRD status of all subjects will be evaluated during cycles 3, 6, 9, 12, 15, 18, 21, and 24. If subjects achieve U-MRD status in the peripheral blood, MRD will again be assessed by peripheral blood 4 weeks later to confirm U-MRD. Subjects will remain on study treatment through 24 cycles or the occurrence of confirmed U-MRD response in the peripheral blood, after which they will enter a period of treatment-free observation.

Following achievement of U-MRD, subjects will enter a period of treatment-free observation (TFO) with serial MRD assessments every 12 weeks up to Cycle 24 then every 24 weeks thereafter, unless clinically indicated sooner.

Subjects who do not achieve confirmed U-MRD will continue treatment until the completion of 24 cycles of treatment, definitive disease

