3.2 EFFICACY ENDPOINTS

Undetectable Minimal Residual Disease (U-MRD) Rate

U-MRD rate is defined as the proportion of subjects who have undetectable MRD in the peripheral blood as confirmed by central lab.

Time to U-MRD

Time to undetectable minimal residual disease is defined as the interval from enrollment to the first assessment of U-MRD.

Overall response rate (ORR)

ORR is defined as sum of CR and PR rates.

Complete Response (CR) Rate

CR rate is defined as the proportion of subjects who achieve a CR.

Progression-free survival (PFS)

[figure not shown]
PFS is defined as the interval from enrollment to the earlier of the first documentation of definitive disease progression or death from any cause.

Definitive disease progression based on standard criteria (Hallek, et al., 2018) and occurring for any reason (i.e., increasing lymphadenopathy, organomegaly or bone marrow involvement; decreasing platelet count, hemoglobin, or neutrophil count; or worsening of disease-related symptoms). Note that lymphocytosis in the absence of other evidence of disease progression does not constitute disease progression.

Time to second objective disease progression (PFS2)

PFS2 is defined as the interval from enrollment to the earlier of the first documentation of definitive disease progression on next-line treatment or death from any cause.

Definitive disease progression based on standard criteria (Hallek, et al., 2018) and occurring for any reason (i.e., increasing lymphadenopathy, organomegaly or bone marrow involvement; decreasing platelet count, hemoglobin, or neutrophil count; or worsening of disease-related symptoms). Note that lymphocytosis in the absence of other evidence of disease progression does not constitute disease progression.

Duration of U-MRD response

Duration of U-MRD response is defined as the interval from the first documentation of undetectable MRD to the earlier of the first documentation of presence of MRD or death from any cause.

Treatment-free survival (TFS)

TFS is defined as the interval from drug discontinuation to the earlier of initiation of retreatment for disease progression requiring treatment or death from any cause.

Disease progression requiring treatment is based on standard criteria (Hallek, et al., 2018)

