5.6 DISCONTINUATION FROM STUDY

Subjects will be discontinued from the study for any of the following reasons:

- Disease progression while on study treatment
- Disease progression within 6 months during treatment-free observation
- Subject requests to withdraw consent or discontinue treatment
- Pregnancy
- Inability of the subject to comply with study requirements
- Conditions requiring therapeutic intervention not permitted by the protocol
- Non-compliance/lost to follow-up
- Investigator discretion
- Discontinuation of the study by the Sponsor

Subjects who discontinue from study treatment (for reasons other than progressive disease) will continue to be followed for progression and survival for 24 months.

After withdrawal from study, subjects should be followed for AEs for 30 calendar days after their last dose of either study drug. All new AEs occurring during this period must be reported and followed until resolution, unless, in the opinion of the investigator, these values are not likely to improve because of the underlying disease. In this case the investigators must record his or her reasoning for this decision in the subject's medical records and as a comment on the electronic Case Report Form (eCRF).

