7.2 STUDY ASSESSMENT AND TREATMENT SCHEDULE - TREATMENT FREE OBSERVATION

Cycle = 28 days	Treatment-Free Observation (TFO) Visits ¹	
Procedures/Days ²	TFO1 Cycle 1 Day 1	TFO Subsequent Day 1 Every 3 Cycles for 24 cycles and every 6 cycles thereafter
ECOG	X	X
Physical Examination	X	X
Vital Signs ³	X	X
Hematology	X	X
Chemistry	X	X
PB MRD ⁴		X
AE Evaluation	X	X
Con Meds	X	X

¹ At completion of 24 cycles with no progression of disease (POD), confirmed U-MRD, or discontinuation of treatment due to toxicity in absence of POD, subjects will enter a treatment-free observation period. Study assessments will be completed every 3 cycles for 24 cycles from discontinuation of any study drug.

² All TFO visits have a +/- 14 day window.

³ Vital signs to include temp, BP, HR, and respirations

⁴ Subjects on treatment-free observation with U-MRD should have peripheral blood MRD assessments approximately every 12 weeks +/- 2 weeks prior to Cycle 24 and every 24 weeks +/- 2 weeks, unless clinically indicated sooner, after Cycle 24. For subjects entering treatment-free observation with D-MRD, no PB MRD is required. For subjects entering TFO due to discontinuation of treatment due to toxicity in absence of POD, MRD should be done at TFO1. If U-MRD repeat MRD in PB in 4 weeks, if D-MRD, no further PB MRD is required.

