11.6.1 STATISTICAL ANALYSES

11.6.1.1 PRIMARY EFFICACY ENDPOINT

Best overall U-MRD rate will be reported as well as a proportion during cycles 3, 6, 9, 12, 15, 18, 21 and 24. The U-MRD rate is defined as the proportion of subjects with detectable MRD at baseline who convert to U-MRD in the peripheral blood on two sequential peripheral blood studies at least 4 weeks apart post-baseline. Subjects with detectable MRD at baseline who do not have an MRD assessment at any post-baseline visits will be considered non-responders and will be included in the denominator when calculating U-MRD rate. The 95% confidence intervals (Clopper-Pearson) for the MRD negativity rate will be presented.

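### Time to U-MRD: Kaplan-Meier censors subjects who die or progress before converting, so the curve can end above the observed conversion proportion, and the event wording does not clearly require confirmation

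*Combined protocol and SAP*

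**What the plan says.** Section 3.2, repeated in 11.6.1.2.1, defines the endpoint: "Time to undetectable minimal residual disease is defined as the interval from enrollment to the first assessment of U-MRD". The estimator is Kaplan-Meier, and the censoring rule is "For subjects who do not achieve U-MRD, it will be censored at the last MRD assessment". Nothing is said about death or progression before U-MRD. By contrast, the PFS, PFS2, duration of U-MRD and treatment-free survival definitions in 11.6.1.2 all name death as an event.

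The primary endpoint (11.6.1.1) counts subjects "who convert to U-MRD in the peripheral blood on two sequential peripheral blood studies at least 4 weeks apart post-baseline". It also rules that "Subjects with detectable MRD at baseline who do not have an MRD assessment at any post-baseline visits will be considered non-responders", and keeps them in the denominator. Section 11.2 has a similar rule for subjects with no disease assessment after baseline.

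The synopsis (Study Duration) separates the first negative from its confirmation: "If subjects achieve U-MRD status in the peripheral blood, MRD will again be assessed by peripheral blood 4 weeks later to confirm U-MRD". Where the pair is meant it says so: "Subjects who do not achieve confirmed U-MRD will continue treatment until the completion of 24 cycles of treatment".

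On leaving MRD follow-up:
- Section 5.6 lists "Disease progression while on study treatment" among the reasons for leaving the study.
- For a subject who stops for toxicity and is tested at the first treatment-free visit (TFO1), Section 7.2 footnote 4 says "If U-MRD repeat MRD in PB in 4 weeks, if D-MRD, no further PB MRD is required".
- Stopping only one drug need not end treatment (8.4.1), so it is not counted as an exit here.

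**The concern.** Kaplan-Meier gives each censored subject the later conversion experience of those who remain. That suits a subject still being tested at data cut-off. It does not suit one who has died, or who has left the study for progression, because that subject can no longer be seen to convert on study. Reading one minus Kaplan-Meier as the share who convert then overstates that share.

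Two smaller mismatches with the primary sit beside this. The event may be a single negative rather than a confirmed pair. Subjects with no MRD test after baseline would drop out of the risk set at the start, although the primary counts them as failures.

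The endpoint answers a named secondary objective (3.1). The design stops treatment on depth of response, so readers will use this curve to judge how long the triplet is needed. Cohorts hold about 28 subjects at most and there is no control arm, so a handful of exits can move the curve.

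**Working it through.** The plan states no expected rate or median for this endpoint, so there is no figure to reproduce. All rates below are assumed. From the documents come the eight MRD tests (cycles 3 to 24, every three 28-day cycles; 7.1 footnote 7), the cohort size of 28 (synopsis), and the censoring and event rules above.

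**Direction.** Kaplan-Meier starts each of N subjects with weight 1/N and passes a censored subject's weight to those still at risk. Every converter therefore carries at least 1/N, and at the end of follow-up 1−KM ≥ events/N. Equality holds when no one is censored before a later event. A check on 40,000 random cohorts of 5 to 28 subjects, each on nominal visits and with dates shifted by up to 14 days, compared 1−KM on first negatives with the confirmed proportion at end of follow-up. Of 80,000 comparisons, 0 were below, 6,982 equal and 73,018 above.

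**Size, large-sample model.** Before each test a share k leaves by progression or death; those remaining convert with probability h.
- 1−KM = 1 − (1−h)^8.
- Cumulative incidence = h(1−k)(1−r^8)/(1−r), with r = (1−k)(1−h).

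For h = 0.08, 1−KM = 1 − 0.92^8 = 0.487. For k = 0.03, r = 0.97 × 0.92 = 0.8924 and r^8 = 0.4022, so cumulative incidence = 0.0776 × 0.5978 / 0.1076 = 0.431.

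| h per test | 1−KM | k = 1% | k = 3% | k = 6% |
|---|---|---|---|---|
| 5% | 33.7% | 32.3% | 29.7% | 26.2% |
| 8% | 48.7% | 46.7% | 43.1% | 38.2% |
| 12% | 64.0% | 61.6% | 57.1% | 51.0% |

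Without conversion, these k mean 8%, 22% and 39% gone over eight tests (1 − (1−k)^8). If half the exits are instead toxicity stops who get the TFO1 test, the 8% row becomes 47.0%, 43.8% and 39.4%.

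**Size, one cohort of 28.** Take 12 confirmed converters (12/28 = 42.9%) at tests 1 to 8 as 3, 2, 2, 2, 1, 1, 1, 0. With one exit before each of tests 1 to 6:

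KM = 24/27 × 21/23 × 18/20 × 15/17 × 13/14 × 11/12 × 10/11 = 0.4987, so 1−KM = 50.1%.

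With all six exits after the last conversion, 1−KM = 42.9%. Over all placements of exits:

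| Exits | Mean 1−KM | Range | Placements showing a median |
|---|---|---|---|
| 3 | 45.3% | 42.9–48.0% | 0% |
| 6 | 48.3% | 42.9–54.5% | 16% |
| 9 | 52.2% | 42.9–63.2% | 82% |

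**Event.** With 12 confirmed converters and no exits, 1, 2 or 3 first negatives that are never confirmed give 13/28 = 46.4%, 14/28 = 50.0% or 15/28 = 53.6%, against 42.9%. A failed negative that is confirmed at a later scheduled test leaves the end of the curve unchanged but is dated about 3 × 28 = 84 days (12 weeks) early. If the plan means the confirmed pair, neither effect arises.

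**No MRD test after baseline.** With 13 converters (13/28 = 46.4%), 1, 2 or 3 such subjects leaving the risk set at the start give 13/27 = 48.1%, 13/26 = 50.0% or 13/25 = 52.0%.

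**The case against.** The plan does not say that 1−KM will be reported as a U-MRD rate. The rate comes from 11.6.1.1, overall and by visit, with everyone in the denominator, so a reader has the right proportion beside the curve. Time to conversion with leavers censored can also be defended as a different target: conversion had nobody left. This stands in part, and the choice is one of estimand. But the plan does not state that target, and it would need exits to be unrelated to the chance of converting, which is hard to assume for progression.

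A reader might infer that every bias in this endpoint favours faster or higher conversion. The documents do not support that. Tests about 12 weeks apart date a conversion late. As an estimate of conversion had nobody left, the curve could err either way. If actual dates are read at nominal cycle days and set against visit-labelled proportions, the curve can fall below: this happened in 6,838 of 40,000 landmark checks with dates shifted by up to 14 days. The inequality holds only like for like, at end of follow-up or at the same visit.

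A reader might also infer that the plan definitely counts unconfirmed negatives. The synopsis usage points that way but is not uniform, since entry to treatment-free observation is also described without the word confirmed. The phrase could mean the first sample of the confirmed pair.

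On size, entry requires stable disease or better on current therapy (4.1), and nothing in the documents supports 6% leaving per test. At 1% the gap is 1.9 points. In the cohort of 28, one or two exits give a mean of 43.6% or 44.5% against 42.9%, with no median in any placement. The exact 95% interval for 12/28, 24.5% to 62.8%, is far wider than that. This stands, and it limits the priority.

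Finally, 11.2 already calls subjects with no disease assessment after baseline non-responders. It sets no time or censoring rule for this curve, so it does not settle the matter.

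**Conclusion.** The point holds for the estimator. Followed as written, 11.6.1.2.1 censors subjects who die or progress before U-MRD, and at end of follow-up 1−KM equals or exceeds the observed conversion proportion. It exceeds it whenever a subject is censored before a later conversion. At an assumed 8% conversion per test, the excess over cumulative incidence is about 2, 6 or 10 points at 1%, 3% or 6% exits per test, and nil if all exits come last.

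The event wording is a real ambiguity, but only a clarification if the confirmed pair is intended. The handling of subjects with no test after baseline is an inference from the censoring rule, which does not mention them.

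A reader might infer that the primary result is inflated, or that a median will appear although fewer than half convert. Neither follows. The primary rate has its own rule and is unaffected. In the example such a median needs a true rate just under half and about six or more exits, suitably timed. The endpoint is descriptive, with no test or decision attached. Confidence is high in the mechanism and low in the size. Priority: low to moderate.

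**What to change.** In 3.2 and 11.6.1.2.1:
- Define the event as confirmed U-MRD, dated at the first of the two samples.
- Replace Kaplan-Meier with cumulative incidence (Aalen-Johansen) in the ITT population, with death and progression before confirmed U-MRD as competing events.
- Count as non-converters, kept in the denominator: subjects with no MRD test after baseline; toxicity stops still D-MRD after the TFO1 test and any 4-week repeat; and subjects who withdraw or are lost without confirmed U-MRD.
- Censor only subjects still in MRD follow-up at data cut-off. Subjects who finish 24 cycles with detectable MRD then also count as non-converters.

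The rule for withdrawals matters. If all six exits in the 28-subject example were withdrawals and were censored, Aalen-Johansen would give 50.1%, the same as Kaplan-Meier, against 42.9% observed. With three progressions or deaths and three censored withdrawals it would give 46.0% to 46.6%, depending on order.

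The cost is a few sentences and standard software, with no extra samples or visits. The curve may look less favourable, and it will describe observed conversion rather than conversion had nobody left.

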11.6.1.2.2 OVERALL RESPONSE RATE

ORR will be determined according to the criteria of the International Workshop on Chronic Lymphocytic Leukemia (Hallek et al. 2018).

Overall Response Rate (ORR) is defined as percent of subjects who achieve CR or PR. Best ORR may be reported as well as a proportion during the first 6, 12, 18 and 24 cycles. The 95% confidence intervals for the response rates will be presented. Additional logistic analyses model may be used to assess the impact of demographic and baseline parameters.

11.6.1.2.3 COMPLETE RESPONSE RATE

CR rate is defined as the percent of subjects who achieve a CR. CR may be reported as a proportion during the first 6, 12, 18 and 24 cycles and overall. The 95% confidence intervals will be presented. Additional logistic analyses model may be used to assess the impact of demographic and baseline parameters.

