Inclusion Criteria	
Subjects must meet all the following inclusion criteria to be eligible for participation in this study. Eligibility criteria must be met at screening and at Cycle 1 Day 1 prior to dosing.
 
 1. Subjects with CLL who are currently receiving treatment with ibrutinib, acalabrutinib or venetoclax for greater than or equal to 6 months. 2. Minimal residual disease (MRD) positive (D-MRD) as determined by central lab performed during the screening period. 
 a. For subjects receiving venetoclax: response assessment demonstrating stable disease, partial response, or complete response following initiation of current venetoclax therapy AND detectable MRD in the peripheral blood (central lab). b. For subjects receiving ibrutinib or acalabrutinib: response assessment demonstrating stable disease, partial response or partial response with lymphocytosis, or complete response AND detectable MRD in the peripheral blood (central lab). 3. Adequate organ system function, defined as follows: 
 a. Absolute neutrophil count (ANC) $\geq 1,000/\text{mm}^3$ (μL) / platelet count $\geq 50,000/\text{mm}^3$ (μL). Growth factor to maintain these counts is permitted during screening period and throughout the conduct of the trial. b. Total bilirubin ≤ 1.5 times the upper limit of normal (ULN), unless a diagnosis of Gilbert's syndrome or an autoimmune hemolytic anemia. c. Alanine aminotransferase (ALT) and aspartate aminotransferase (AST) $\leq 2.5 \times$ ULN if no liver involvement or $\leq 5 \times$ the ULN if known liver involvement. d. Calculated creatinine clearance $>30 \text{ mL/min}$ (as calculated by the modified Cockcroft-Gault formula, MDRD formula, or 24-hour urine CrCl). 4. ECOG performance status ≤ 2. 5. Male or female ≥ 18 years of age. 6. Ability to swallow and retain oral medication. 7. Female subjects who are not of child-bearing potential (see Appendix B- Contraceptive Guidelines and Pregnancy), and female subjects of child-bearing potential who have a negative serum pregnancy test within 3 days prior to Cycle 1, Day 1. Female subject of child-bearing potential, and male partners must consent to use a medically acceptable method of contraception throughout the study period and for 4 months after the last dose of ublituximab or umbralisib, and for at least 30 days after the last dose of ibrutinib, acalabrutinib or venetoclax.

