4.1 INCLUSION CRITERIA

1. Subjects with CLL who are currently receiving treatment with ibrutinib, acalabrutinib or venetoclax for greater than or equal to 6 months.
2. Minimal residual disease (MRD) positive (D-MRD) as determined by central lab performed during screening period.
 - a. For subjects receiving venetoclax: response assessment demonstrating stable disease, partial response, or complete response AND detectable MRD in the peripheral blood (central lab).
 - b. For subjects receiving ibrutinib or acalabrutinib: response assessment demonstrating stable disease, partial response or partial response with lymphocytosis, or complete response AND detectable MRD in the peripheral blood (central lab).
3. Adequate organ system function, defined as follows:
 - a. Absolute neutrophil count (ANC) $\geq 1,000/\text{mm}^3$ (μL) / platelet count $\geq 50,000/\text{mm}^3$ (μL). Growth factor to maintain these counts is permitted during screening period and throughout the conduct of the trial.
 - b. Total bilirubin ≤ 1.5 times the upper limit of normal (ULN), unless a diagnosis of Gilbert's syndrome or an autoimmune hemolytic anemia.
 - c. Alanine aminotransferase (ALT) and aspartate aminotransferase (AST) $\leq 2.5 \times \text{ULN}$ if no liver involvement or $\leq 5 \times \text{the ULN}$ if known liver involvement.
 - d. Calculated creatinine clearance $>30 \text{ mL/min}$ (as calculated by the modified Cockcroft-Gault formula, MDRD formula, or 24-hour urine CrCl).
4. ECOG performance status ≤ 2 .
5. Male or female ≥ 18 years of age.
6. Ability to swallow and retain oral medication.
7. Female subjects who are not of child-bearing potential (see Appendix B- Contraceptive Guidelines and Pregnancy), and female subjects of child-bearing potential who have a negative serum pregnancy test within 3 days prior to Cycle 1, Day 1. Female subjects of child-bearing potential, and male partners must consent to use a medically acceptable method of contraception throughout the study period and for 4 months after the last dose of ublituximab or umbralisib, and for at least 30 days after the last dose of ibrutinib, acalabrutinib or venetoclax.
8. Willingness and ability to comply with trial and follow-up procedures and give written informed consent.

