10.2 IDENTIFICATION AND MEASUREMENT OF TUMOR LESIONS AND ORGANOMEGLY

10.2.1 TARGET LESIONS

Measurable disease is not a requirement for study enrollment. For subjects with measurable disease at baseline, up to 6 lymph nodes should be selected as target lesions that will be used to quantify the status of the disease during study treatment. Ideally, the target lesions should be in disparate regions of the body. Only peripheral nodes need be selected as target lesions. However, it is optimal if mediastinal and retroperitoneal areas of disease are assessed whenever these sites are involved.

Target lesions will be measured and recorded at baseline and as per the study assessment schedule. The cross-sectional dimensions (the largest cross-sectional diameter, i.e., the LD \times LPD) will be recorded (in cm) for each target lesion. The product of the perpendicular diameters (PPD) (in cm²) for each target lesion and the sum of the products (SPD) (in cm²) for all target lesions will be calculated and recorded. The baseline SPD will be used as

references by which objective tumor response will be characterized during treatment. The nadir LD of individual lesions and the nadir SPD will be used as references by which CLL progression will be characterized. All LD and LPD diameters will be reported in centimeters and all PPDs and SPDs will be reported in centimeters squared.

A nodal mass may be selected as a measurable nodal target lesion if it is > 1.5 cm in long axis diameter and > 1.0 cm in short axis diameter. At follow-up time points, the LDs for individual lesions and the SPD of all nodal target lesions will be considered.

A new node that measures > 1.5 cm in the LD and > 1.0 cm in the LPD will be considered progressive disease.

In cases in which a large lymph node mass has split into multiple components, all subcomponents regardless of size will be used in calculating the SPD. Progression of the lesion will be based on the SPD of sub-components. Lesion sub-components will have the true PPDs calculated. Similarly, lesion sub-components that are visible but neither abnormal nor measurable will have the default PPD of 1.0 cm^2 ($1.0\text{ cm} \times 1.0\text{ cm}$) used in calculating the SPD.

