10.4 COMPLETE RESPONSE

To satisfy criteria for a CR, all of the following criteria must be met:

- No evidence of new disease
- ALC in peripheral blood of $<4 \times 10^9/L$
- Regression of all target nodal masses to normal size ≤ 1.5 cm in the LD
- Normal spleen and liver size

- Regression to normal of all nodal non-target disease and disappearance of all detectable non-nodal, non-target disease
- Peripheral blood counts meeting all of the following criteria:
 - ANC $>1.5 \times 10^9/L$ without need for exogenous growth factors (e.g., G-CSF)
 - Platelet count $\geq 100 \times 10^9/L$ without need for exogenous growth factors
 - Hemoglobin $\geq 110 \text{ g/L}$ (11.0 g/dL) without red blood cell transfusions or need for exogenous growth factors (e.g., erythropoietin)

Subjects who fulfill all the criteria for a CR but who have a persistent anemia, thrombocytopenia, or neutropenia or a hypocellular bone marrow that is related to prior or ongoing drug toxicity (and not to CLL) will be considered as a CR with incomplete marrow recovery (CRi).

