17 APPENDIX A – CLL RESPONSE DEFINITION

Assessment of response will follow the guidelines published by Hallek et al. (2018).

Assessment of response should include a careful physical examination and evaluation of the blood and marrow.

Table 4 - Response definition after treatment for CLL patients

GROUP	PARAMETER	CR	PR	PD	SD
A	Lymph nodes	None \geq 1,5 cm	Decrease \geq 50% (from baseline) ¹⁾	Increase \geq 50% from baseline or from response	Change of -49% to +49%
	Liver and/or spleen size*	Spleen size $<$ 13 cm; liver size normal	Decrease \geq 50% (from baseline)	Increase \geq 50% from baseline or from response	Change of -49% to +49%
	Constitutional symptoms	None	Any	Any	Any
	Circulating lymphocyte count	Normal	Decrease \geq 50% from baseline	Increase \geq 50% over baseline	Change of -49% to +49%
B	Platelet count	\geq 100.000/ μ l	\geq 100.000/ μ l or increase \geq 50% over baseline	Decrease of \geq 50% from baseline secondary to CLL	Change of -49 to +49%
	Hemoglobin	\geq 11,0 g/dl (untransfused and without erythropoietin)	\geq 11 g/dl or increase \geq 50% over baseline	Decrease of \geq 2 g/dl from baseline secondary to CLL	Increase $<$ 11,0 g/dl or $<$ 50% over baseline, or decrease $<$ 2 g/dl
	Marrow	Normocellular, no CLL cells, no B-lymphoid nodules	Presence of CLL cells, or of B-lymphoid nodules, or not done	Increase of CLL cells by \geq 50% on successive biopsies	No change in marrow infiltrate

1) Sum of the products of 6 or less lymph nodes (as evaluated by CT scans and physical exam in clinical trials, or by physical exam in general practice).

CR, complete remission: all of the criteria have to be met; PR, partial remission: for a PR at least 1 of the parameters of group A and 1 parameter of group B need to improve if previously abnormal. If only one parameter of both groups A and B is abnormal prior to therapy, only 1 needs to improve. PD, progressive disease: at least one of the above criteria of group A or group B has to be met; SD, stable disease: all of the above criteria have to be met. Constitutional symptoms alone do not define PD.

*Spleen size is considered normal if $<$ 13 cm. There is not firmly established, international consensus of the size of a normal liver; therefore, liver size should be evaluated by imaging and manual palpation in clinical trials and be recorded according to the definition used in a study protocol.

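### Subjects may enter already in complete response, and the initial-phase CR rate and ORR have no rule to keep those pre-existing responses out

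*Combined protocol and SAP*

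**What the plan says.** **Who may enter.** For venetoclax subjects, inclusion criterion 2a in section 4.1 asks for "response assessment demonstrating stable disease, partial response, or complete response AND detectable MRD in the peripheral blood (central lab"; the synopsis version ties that response to the current drug ("complete response following initiation of current venetoclax therapy AND detectable MRD in the peripheral blood (central lab"). For ibrutinib and acalabrutinib subjects, criterion 2b likewise admits "partial response or partial response with lymphocytosis, or complete response AND detectable MRD in the peripheral blood (central lab". Section 10.2.1 adds: "Measurable disease is not a requirement for study enrollment".

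**What counts as CR.** Section 10.4 lists conditions that must all hold: lymphocyte count, node size, spleen and liver size, absence of new disease, and blood counts. Appendix A gives a similar table, including a marrow row, with the note "CR, complete remission: all of the criteria have to be met". One item in 10.4 is worded as change: "Regression of all target nodal masses to normal size".

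**How the rates are formed.** Section 10.3 takes the best response recorded from the start of treatment. Section 11.2 uses all treated subjects for efficacy. Section 11.6.1.2.3 states that "CR rate is defined as the percent of subjects who achieve a CR", and 11.6.1.2.2 defines ORR in parallel as the percentage reaching CR or PR. Both may be reported over the first 6, 12, 18 and 24 cycles, and 95% confidence intervals are to be given.

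**The concern.** The study adds two drugs to a treatment that subjects have already taken for at least 6 months. A reader will take its CR rate and ORR as a description of what happened after that addition. If a CR obtained earlier on ibrutinib, acalabrutinib or venetoclax can be counted again at the first on-study assessment, the rates mix responses that predate the first dose with responses that arose on the triplet, and the planned output gives no means of telling them apart.

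The plan avoids this for its primary endpoint: section 11.6.1.1 counts only subjects who convert from detectable MRD at baseline. It also largely avoids it for PR, which is measured by improvement from the study baseline. CR is the exception.

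**Working it through.** **Step 1: can an entry CR satisfy the on-study definition unchanged?**

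- Most items in section 10.4 describe a state, not a change.
- The nodal item speaks of regression. However, under section 10.2.1 a node "may be selected as a measurable nodal target lesion if it is > 1.5 cm in long axis diameter", whereas CR requires nodes of 1.5 cm or less. A subject in CR at entry has no nodal target that must regress, so the item does not block the carry-over.
- Response is first reassessed at Cycle 3 (section 5.3). A CR still present then is recorded after the start of treatment and qualifies as best response under 10.3.
- Some entry CRs can fail on study: through the marrow requirement (Appendix A; section 7.1, footnote 10), the blood-count thresholds (10.4) or the non-evaluable rules (10.8). None of these concerns entry status, and a subject who passes them all is counted.

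**Step 2: is PR treated alike?** No. Section 10.5 requires improvement from baseline, and section 10 places baseline within 30 days of Cycle 1 Day 1. An unchanged entry PR is therefore stable disease. ORR can thus add inherited CRs to newly earned PRs.

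**Step 3: which phase is affected?** The reporting windows of 6, 12, 18 and 24 cycles match the initial-treatment assessments (Cycles 3, 6, 12, 18, 24; section 5.3), not those of re-treatment (Cycles 7, 14, 20, 26; section 5.5). Re-treatment follows clinical progression, so the problem does not arise there.

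**Step 4: how large could it be?** The plan states no expected CR rate, so there is no figure to reproduce. The only input from the documents is the cohort size, up to about 28 (synopsis, Enrollment). Assumptions:

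- *e* of 28 subjects enter in CR and all persist;
- 4 new CRs occur among the rest;
- intervals are Clopper-Pearson, which the plan names only for the MRD rate.

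Rate as defined = (*e* + 4)/28. Rate among subjects not in CR at entry = 4/(28 − *e*).

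| *e* | As defined (95% CI) | Not in CR at entry (95% CI) | Gap, points |
|---|---|---|---|
| 1 | 5/28 = 17.9% (6.1–36.9) | 4/27 = 14.8% (4.2–33.7) | 3.0 |
| 3 | 7/28 = 25.0% (10.7–44.9) | 4/25 = 16.0% (4.5–36.1) | 9.0 |
| 6 | 10/28 = 35.7% (18.6–55.9) | 4/22 = 18.2% (5.2–40.3) | 17.5 |
| 8 | 12/28 = 42.9% (24.5–62.8) | 4/20 = 20.0% (5.7–43.7) | 22.9 |

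If only 3 of 6 entry CRs persist, the comparison is (3 + 4)/28 = 25.0% against 4/22 = 18.2%. With no new CR at all, the defined rate still has a floor of *e*/28: 3.6%, 10.7%, 21.4% and 28.6% for the four values of *e*.

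**Step 5: does it matter how entry CR is classified?** Suppose 2 of the 6 entry CRs are clinical CRs without marrow confirmation, and both have a clear marrow on study. Excluding all 6 gives 4/22 = 18.2%. Treating those 2 as not in CR at entry, and so as new CRs, gives (4 + 2)/(28 − 4) = 6/24 = 25.0% (9.8–46.7). The all-subject rate stays at 10/28.

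**The case against.** Four arguments deserve weight.

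1. **The outcomes are peripheral.** The only stated objective that names ORR and CR rate concerns re-treatment. The initial-phase rates appear as listed endpoints and other efficacy outcomes, their reporting is partly optional, and no test, threshold or treatment decision rests on them. This stands and limits the severity. It does not remove the point: the rates are defined, given phase-specific windows and assigned confidence intervals.
2. **To *achieve* a CR can mean to attain it newly.** That is a fair reading, but nothing in the plan says so. The defect is a definition that permits the wrong count, not proof that the wrong count will be made.
3. **The large gaps rest on assumed counts.** This is also true. With one entry CR the 3.0-point gap is small beside an interval about 30 points wide.
4. **Without an entry marrow, clearance on study cannot be told from a marrow that was already clear.** This is correct. The 25.0% in step 5 is one end of a bound, not an estimate of new CRs, and should be presented that way.

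The loss is also largely recoverable at reporting, because screening response is collected. However, neither the baseline summaries (11.3) nor the optional logistic models name entry response, so nothing in the plan ensures that it will be used.

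**Conclusion.** The concern holds. Entry in CR is allowed in every cohort, such a CR can still meet the on-study criteria, and neither rate sets an entry-status condition. Followed as written, the plan can report pre-existing CRs as on-study responses in the initial-phase CR rate and ORR.

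The size cannot be known from the documents. It is 3.6 points per persisting entry CR at 28 subjects; the comparison with a rate restricted to subjects not in CR at entry runs from minor to more than 20 points across the assumed range. This should be corrected, but it does not threaten the trial's main conclusion. There is no control arm, so even a restricted rate does not isolate the effect of the added drugs; it only removes responses that already existed.

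**What to change.** In sections 11.6.1.2.2 and 11.6.1.2.3, wherever the initial-phase rates are reported:

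1. Tabulate best on-study response by screening response for each cohort, with maintained CR on its own line and a note that an unchanged entry PR appears as stable disease.
2. Report the CR rate among subjects not in CR at entry, with a Clopper-Pearson 95% interval, and show entry CRs separately within ORR.
3. Keep the all-subject CR rate and ORR as descriptive figures.
4. Classify entry CR from the screening response assessment, using marrow where it was done, and state whether footnote 10 of section 7.1 covers screening. Give clinical entry CRs without marrow confirmation their own row, and present the rate in item 2 with that row excluded and included, labelled as bounds.

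**Cost.** Wording and one table, plus the second version of the restricted rate. The screening response assessment is already required. The restricted interval is wider: with 4 new CRs it spans 28.6 points at 4/28 (4.0–32.7%) and 35.1 points at 4/22 (5.2–40.3%). Cells will be small in cohorts of about 28. Where no entry marrow exists, some misclassification remains possible in either direction.
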